COVER PAGE:

Brief Title: ROP Check Database Premature Infant Outcomes

NCT Number: not yet assigned

Unique Protocol ID: ROPCHECK24

Study Protocol and Statistical Analysis Plan

This study has IRB review and does NOT require consent.

Investigator: [name]

Observation trial of de-identified data from large ongoing US clinical dataset covering academic and private hospitals.

Data reviewed concerning those infants who progressed to threshold for therapy (Type 1) and what type of therapy delivered.

Statistics are typical descriptive statistics from database including median, interquartile range and percentages.

These are analyzed with Mann-Whitney, Kruskal-Wallis and Chi Square.

The workflow (encounter volume) for each infant is analyzed.

The AAP guideline ROP screening criteria are evaluated in light of other recent proposals and compared to the ROP Check® dataset.

“ROP Check® (NeoLight, LLC, Phoenix, Arizona) is a cloud-based electronic medical record (EMR) with built-in decision support used for ensuring ROP exams occur in a timely manner assisting neonatologists conform to complex screening guidelines, and for ophthalmologist tracking ROP staging exams and treatment. We use a de-identified data set of examination results from 28 hospitals which employed the software from 2010 through 2022. The acuity level of the neonatal intensive care units (NICUs) is as follows: four Level 4 NICUs, six Level 3B NICUs, twelve Level 3 NICUs, and six Level 2 NICUs and included both academic and non-academic centers. The American Academy of Pediatrics ROP guidelines recommend all infants less than 31 weeks gestational age (“a gestational age of 30 or less [completed weeks] (as defined by the neonatologist”) require

ROP staging exams¹. Surviving infants with birth gestational age of 21+6 weeks to 30+6 weeks are included in the analysis. IRB exemption (45 CFR § 46.104(d)(4),) was obtained for using the de-identified data set from WCG IRB on 3/4/24. The study complies with the Declaration of Helsinki and the Health Insurance Portability and Accountability Act (HIPAA). Hospitals initiated the use of the program at different years. The infant's race is diagnosed by the neonatologist was recorded by NICU clinical staff.

Patient demographic characteristic data, such as birthweight and gestational age, and details of numbers and timing of recorded encounters (either examinations or treatments) in ROP Check® are analyzed for non-normal distribution by Shapiro Wilk test before non-parametric analysis.

Recently proposed alterations to the AAP screening guidelines have been published but until now, not yet compared with a North American cohort of premature infants with substantial numbers of infants of Pacific races that are at high risk for treatment-warranted ROP²⁻⁵ .

Compared study cohorts							ROP Check® from 2010 to 2022									
Study	Years	patients	BW>	GA>	1st exam?	miss ?	missed ?	Avoid ?	Cohort	Treat	%Tx	Tx GA		%ROP	Pacific	
E-ROP	2004-22	1257 of 6729	750	27	37 wk	1	4	2.0%	2975	32	1.1 %	33.6	41.6	80%	15%	
First-ROP	2017-23	1125 of 2004	800	27	34 wk	0	4	8.6%	2917	29	1.0 %	33.6	41.6	80%	47%	
Moir +	2003-22	6025 of 8364	1000	29	31-34 wk	0	4	3.1%	1543	4	0.3 %	36.1	37.9	90%	50%	
SCREEN-ROP	2016-24	61 of 823	1200	30	31-34 wk	0	2	"7.6%" "	625	2	0.3 %	37.5	37.7	94%	22%	
TWO-ROP	2013-23	1095 of 3239	1500	30	38-9 wk	0	3	2.2%	989	3	0.3 %	37.5	37.9	91%	21%	
ROP Check®										5058	387	7.7 %	29.1	47.7	59%	13%
"30+4"	2010-22	287 of 5058	any	30+4	31-34 wk	na	0	2.5%	287	0	0.0 %	na	na	93%	25%	

ROP-if-P	2010-22	957 of 5058	140	0	30	31-34 wk	na	0	7.90%	957	0	0.0 %	na	na	92%	0%
----------	---------	-------------	-----	---	----	----------	----	---	-------	-----	---	-------	----	----	-----	----

References:

1. Fierson WM, Ophthalmology AAOPSo, American Academy Of O, American Association For Pediatric O, Strabismus, American Association Of Certified O. Screening Examination of Premature Infants for Retinopathy of Prematurity. *Pediatrics*. Dec 2018;142(6):doi:10.1542/peds.2018-3061

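### Screening rules are compared on 0 to 4 missed infants each with no planned intervals, so '0 missed' does not separate two rules from the other five; the named tests also treat infants from 28 hospitals as independent

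*Combined protocol and SAP*

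**What the plan says.** The cover page gives the whole statistical method in two sentences: "Statistics are typical descriptive statistics from database including median, interquartile range and percentages" and "These are analyzed with Mann-Whitney, Kruskal-Wallis and Chi Square". A Shapiro-Wilk check precedes the non-parametric analysis. No interval estimate is mentioned.

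One aim is the comparison of screening rules: "The AAP guideline ROP screening criteria are evaluated in light of other recent proposals and compared to the ROP Check® dataset". The stated reason is that the recent proposals are "not yet compared with a North American cohort of premature infants" that includes substantial numbers of infants of Pacific races. The table of compared study cohorts then gives, for each rule, a cohort size within ROP Check, a count under 'missed ?', a treated count and a treated percentage. It also has a separate 'miss ?' column, apparently for the source study (an inference). Neither miss column is defined. For '30+4' and ROP-if-P the 'miss ?' entry is 'na'.

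On the data source: "We use a de-identified data set of examination results from 28 hospitals which employed the software from 2010 through 2022". The units are "four Level 4 NICUs, six Level 3B NICUs, twelve Level 3 NICUs, and six Level 2 NICUs", and "Hospitals initiated the use of the program at different years". Encounter volume is also an analysis target: "The workflow (encounter volume) for each infant is analyzed". The plan does not say how hospital enters any analysis.

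**The concern.** A count of zero invites a firm reading. In this table two rules show 0 missed and five show 2 to 4, with no measure of precision beside them. A reader choosing between rules could take the zeros as evidence of greater safety. What matters is whether cohorts of 287 and 957 infants can carry that reading. The two zeros also come only from the 5,058 ROP Check infants, with no published result to set against them.

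The second issue concerns the tests. Mann-Whitney, Kruskal-Wallis and chi-square in their standard forms take each infant as an independent observation. Infants in one hospital share examiners, scheduling and treatment habits, so encounter counts and therapy type may be correlated within a hospital. If so, p-values for factors that differ between hospitals would be too small.

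**Working it through.** **Inputs.** From the table of compared study cohorts: cohort, treated and 'missed ?' counts per rule. From the data-source paragraph: 28 hospitals. The documents give no intraclass correlation (ICC).

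**Step 1: reproduce the plan's own figures.** Treated percentage = treated / cohort. 32/2975 = 1.08%, 29/2917 = 0.99%, 4/1543 = 0.26%, 2/625 = 0.32%, 3/989 = 0.30%, 387/5058 = 7.65%, and 0/287 and 0/957 = 0%. All eight round to the printed values, so these columns have been read correctly.

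**Step 2: exact (Clopper-Pearson) 95% intervals for missed / cohort.** For x events in n, the lower limit is the 2.5% quantile of Beta(x, n − x + 1) and the upper limit the 97.5% quantile of Beta(x + 1, n − x). For x = 0 the upper limit is 1 − 0.025^(1/n).

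| Rule | Missed / cohort | Estimate | 95% interval |
|---|---|---|---|
| E-ROP | 4/2975 | 0.134% | 0.037 to 0.344% |
| First-ROP | 4/2917 | 0.137% | 0.037 to 0.351% |
| Moir + | 4/1543 | 0.259% | 0.071 to 0.662% |
| SCREEN-ROP | 2/625 | 0.320% | 0.039 to 1.151% |
| TWO-ROP | 3/989 | 0.303% | 0.063 to 0.884% |
| '30+4' | 0/287 | 0% | 0 to 1.277% |
| ROP-if-P | 0/957 | 0% | 0 to 0.385% |

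For the zeros: 1 − 0.025^(1/287) = 1.277%, about 1 in 78; 1 − 0.025^(1/957) = 0.385%, about 1 in 260. Both exceed the largest of the other five estimates, 0.320%.

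**Step 3: how surprising is a zero?** If the true risk under a zero-miss rule equalled one of the other five estimates r, taken as known, the chance of seeing no miss is (1 − r)^n.

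| r | n = 287 | n = 957 |
|---|---|---|
| 0.134% | 0.68 | 0.28 |
| 0.137% | 0.67 | 0.27 |
| 0.259% | 0.48 | 0.083 |
| 0.303% | 0.42 | 0.055 |
| 0.320% | 0.40 | 0.047 |

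A zero is unremarkable for '30+4'. For ROP-if-P it would be fairly unusual at the higher rates. Those rates are themselves uncertain, resting on 2 to 4 events.

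**Step 4: clustering, illustration only.** Assume equal hospital sizes: m = 5058/28 = 180.6. The design effect is 1 + (m − 1) × ICC. For assumed ICCs of 0.001, 0.01 and 0.05 it is 1.18, 2.80 and 9.98. A nominal 5% test of a factor that varies only between hospitals would then have a true error rate of about 7%, 24% and 54%. Factors spread evenly within hospitals would be affected far less.

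For the zero counts, applying the same formula to 287/28 and 957/28 infants per hospital moves the upper limits only to 1.29%, 1.39% and 1.86% for '30+4', and to 0.40%, 0.51% and 1.02% for ROP-if-P. For those two rows at small ICC, the missing interval matters more than the clustering.

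**Step 5: what the undefined columns can mean.** 'Missed ?' equals treated for five rules, but is 4 against 32 for E-ROP and 4 against 29 for First-ROP. Read the two 'Tx GA' values as the range of age at treatment, an inference that the whole-cohort row (29.1, 47.7) fits. In TWO-ROP, treatment at 37.5 to 37.9 weeks precedes a first exam listed at 38-9 weeks, so all 3 would be missed. In E-ROP and First-ROP, treatment spans 33.6 to 41.6 weeks against first exams at 37 and 34 weeks, so only some would be missed. For the four rules listed at 31-34 weeks, missed equals treated, which fits exemption from screening.

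**The case against.** The best defence is that this is a short descriptive database study. It nowhere says that '30+4' or ROP-if-P is safer, and it prints 287 and 957 beside the zeros. That is true, and the over-reading remains a risk rather than something the plan asserts. But the plan goes beyond description: it names hypothesis tests and makes the evaluation of screening rules an aim, and a printed denominator does not tell a reader how far a zero can be trusted.

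Three stronger readings are tempting and not supported.

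- A reader might infer that 4 missed against 32 or 29 treated is an internal contradiction, or that the choice of definition reverses the result. On treated / cohort, E-ROP (0.737 to 1.515%) and First-ROP (0.667 to 1.425%) do lie above the ROP-if-P upper limit of 0.385%. But treated and missed are differently labelled outcomes, and the exam and treatment ages are consistent with missed meaning treated before a deferred first exam. What is lacking is a footnote.
- A reader might infer that chi-square will be applied to the miss counts. The documents do not assign any test to them, so no wrong test or false significance can be alleged there. A paired test over all 5,058 infants would not be a good substitute either: it ignores how many infants each rule spares (287 against 2,975, for instance), and a rule sparing nobody would always score zero.
- A reader might infer that the cut-offs of the two zero-miss rules were tuned on these data. The documents do not say so. If it were the case, the intervals above would be too optimistic.

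On clustering, the objection that its size is unknown and that no between-hospital contrast is stated stands. It limits that part to a request for a method or a stated limitation.

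**Conclusion.** The point holds on precision and, more modestly, on independence. On missed infants, 0/287 (upper limit 1.28%) and 0/957 (upper limit 0.38%) are compatible with the 0.13% to 0.32% estimated for the other five rules, so the table cannot show that a zero-miss rule is safer. The evidence is weakest for '30+4'. This rests on taking missed / cohort as the proportion of interest and on binomial sampling of independent infants. Positive within-hospital correlation would generally widen the intervals.

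The named tests ignore 28 hospitals of four acuity levels with staggered entry. The direction of the risk is clear for factors that differ between hospitals. Its size rests entirely on an ICC that the documents do not give. The undefined miss columns are a minor omission. The change should be made: it bears directly on what the rule comparison can conclude, and it needs no new infants.

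**What to change.** 1. Report Clopper-Pearson 95% intervals for missed / cohort and treated / cohort for every rule, and note that they ignore hospital clustering. State that a rule with 0 misses will not be described as safer than rules with 2 to 4, and that the two zeros have no outside cohort.
2. List the group comparisons to be tested (encounter volume or therapy type, for example). For these, use a method that accounts for hospital, such as GEE, a mixed model or a cluster bootstrap, if the de-identified file holds a hospital code. If it does not, state non-independence as a limitation and present p-values as descriptive.
3. Footnote 'miss ?' and 'missed ?': the outcome, its timing relative to each rule's first exam, and the denominator.

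The cost is a few lines of text, one footnote and modest code. Stated uncertainty becomes wider, some p-values may become larger, and the '0 missed' headline becomes weaker. The clustered analysis depends on a hospital code that the documents do not confirm.

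### Three screening rules share a printed cut-off of GA>30, but their cohorts of 625, 989 and 957 infants cannot all follow from the cut-offs shown

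*Combined protocol and SAP*

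**What the plan says.** The cover-page description says that the AAP guidelines "recommend all infants less than 31 weeks gestational age" for examination, and quotes the criterion as "a gestational age of 30 or less [completed weeks" (the bracket closes after the last word). It sets the analysis population as follows: "Surviving infants with birth gestational age of 21+6 weeks to 30+6 weeks are included in the analysis".

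The table of compared study cohorts applies each proposed rule to the 5,058 database infants. The cut-off columns are headed "BW> GA> 1st exam". The relevant rows are:

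- SCREEN-ROP: "SCREEN-ROP 2016-24 61 of 823 1200 30"; 625 infants, 2 treated, 22% Pacific.
- TWO-ROP: "TWO-ROP 2013-23 1095 of 3239 1500 30"; 989 infants, 3 treated, 21% Pacific.
- ROP-if-P: birth-weight cell split in extraction and read here as 1400; GA 30; 957 infants, 0 treated, 0% Pacific.
- 30+4: "287 of 5058 any 30+4"; 287 infants, 0 treated, 25% Pacific.

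The documents do not say whether the whole-number GA cut-offs are completed weeks or weeks+0 days, whether the inequality is strict, or whether the weight and age conditions are joined by AND or OR.

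**The concern.** Comparing proposed screening rules with this database is one of the plan's stated purposes, and this table is the only place where the rules are specified. A reader will take the three GA>30 rows as differing in birth weight and, for ROP-if-P, in race. On that reading, raising the weight limit should shrink the group. The table shows the reverse.

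The results at stake are small numbers of events. The rules are judged on 2, 3 and 0 treated infants. At counts this low, a change in who enters a row can change the ranking of the rules, including the in-house rule's result of no treated infant among 957.

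**Working it through.** **Reproducing the plan's figures.** The treated percentages follow from the printed counts: 2/625 = 0.32%, 3/989 = 0.30%, 0/957 = 0.0% and 387/5058 = 7.65%. The divisions are right, so the question is how the denominators were formed. They need patient-level data and cannot be rebuilt from the documents.

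**Check 1: nesting, with no distributional assumption.** Let G be the set of infants meeting GA>30, on whatever scale, and W(x) the set above x grams.

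- AND: W(1500)∩G lies inside W(1200)∩G.
- OR: W(1500)∪G lies inside W(1200)∪G.
- Either way TWO-ROP must hold no more infants than SCREEN-ROP. Printed: 989 against 625.
- The treated infants must nest too. Printed: 3 against 2.
- ROP-if-P (1400 g, 0% Pacific) must also fit inside SCREEN-ROP. Printed: 957 against 625. Against the non-Pacific part only, 625 × 0.78 = about 488.

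The figure of 488 takes the Pacific column as a share of the row's infants. That cannot be true of every row: 0.47 × 2917 = 1,371 (First-ROP) and 0.50 × 1543 = 772 (the GA>29 row) both exceed 0.13 × 5058 = 658, the total for the database. For SCREEN-ROP it is the natural reading, because 22% cannot be a share of 2 treated infants. The comparison of 957 with 625 does not need it.

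**Check 2: level, assuming births spread evenly by day.** The 30+4 row covers two days if strict (30+5, 30+6) or three if not. A cut-off of 30 on a day scale covers six days if strict (30+1 to 30+6) or seven if not.

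| 30+4 row read as | Per day | Six days | Seven days |
|---|---|---|---|
| 3 days | 287/3 = 95.7 | 574 | 670 |
| 2 days | 287/2 = 143.5 | 861 | 1,005 |

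If the inequality is read the same way in both rows, the total is 861 (strict) or 670 (not strict), for infants of any weight. Both are below 957 and 989. Only the mixed reading that gives 1,005 exceeds them, and then 989/1004.5 = 98.5% of infants would have to weigh more than 1500 g. For ROP-if-P, applying the 25% Pacific share of the 30+4 row gives 0.75 × 1004.5 = 753 non-Pacific infants of any weight, still below 957. SCREEN-ROP's 625 lies inside the range and is not anomalous on this check alone.

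This check applies to AND. Under OR, infants could enter on weight alone and the level is not bounded in this way, but Check 1 still fails.

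**Check 3: which GA scale fits.** In completed weeks, GA>30 starts at 31+0 and covers none of the 64 days from 21+6 to 30+6. Under AND it would select nobody. The GA>29, BW>1000 row (1,543 infants) helps to choose. In completed weeks it covers 7 days, 1543/7 = 220 per day. On a day scale it covers 13 days (29+1 to 30+6), 1543/13 = 119 per day. Only the second lies within the 96 to 144 per day implied by the 30+4 row. The day scale is the better fit, and it still does not reconcile the three rows.

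**The case against.** A reader might infer something stronger: that by the plan's own convention no included infant has GA>30, so the three rules are scored on people they could not apply to, and the 30+6 ceiling removes the ages they act on. The documents do not support that. The completed-weeks phrase sits inside the plan's quotation of the AAP criterion and is not declared for the table. Where the plan gives gestational ages of its own it uses weeks+days (21+6, 30+6, 30+4), and the GA>29 row fits a day scale better. No section identifies a rule that acts only from 31+0. The table's rules are presented as alterations to a criterion that already stops below 31 weeks, so a limb starting at 31+0 would change nothing in it.

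Other points on that side also carry weight. Heaping of recorded ages at 30+0 would upset the even-spread calculation. The 1400 g limit is rebuilt from a broken cell, and the printed inequality sign cannot be verified. A published rule may have further criteria that the table omits, which could explain why SCREEN-ROP is small. TWO-ROP also shows a different first-examination time (38-9 wk against 31-34 wk), but ROP-if-P shows the same time as SCREEN-ROP and still exceeds it.

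None of this removes the nesting conflict between 989 and 625, which does not depend on the GA scale, strictness, spread of births or the broken cell. An unlisted criterion would explain the conflict, but it would also confirm that the rows are not defined by what is printed.

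**Conclusion.** The point holds as an internal inconsistency in the table. The SCREEN-ROP, TWO-ROP and ROP-if-P rows cannot all result from one reading of GA>30, one AND or OR rule and the printed weight limits. The excess over the largest possible value is 989 − 625 = 364 infants for TWO-ROP and 957 − 625 = 332 for ROP-if-P (about 957 − 488 = 469 if the Pacific column is a share of infants).

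The nesting result rests on two things only: that all rows draw on the same 5,058 infants, and that no unlisted criterion operates. For ROP-if-P it also rests on the 1400 g reading. The implausibility of 989 and 957 under AND is weaker evidence, because it needs the even-spread assumption. The documents cannot show which row is wrong: SCREEN-ROP may be too small, or the other two too large.

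It is not shown that the true eligible count is zero, or that the 30+6 limit is a design fault. What follows is that treated and missed counts of 2, 3 and 0 should not be compared across these rules until the definitions are settled.

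**What to change.** For each rule in the table, state the GA cut-off in weeks+days, whether the inequality is strict, whether weight and age are joined by AND or OR, and any further criterion (race, examination timing or other) that selects infants. State the denominator of the Pacific column.

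Then re-extract the three rows on those definitions (cohort, treated, missed, %ROP, Pacific) and check nesting across all rows: a stricter rule must not select more infants, or more treated infants, than a looser one. Where an unlisted criterion breaks the nesting, show it in the table. Mark a rule as not evaluable in this cohort only if its stated cut-off selects no infant up to 30+6.

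The cost is a re-run of three rows on existing data and a longer table note. The downside is that the printed counts may change, including the zero treated among 957 for ROP-if-P.

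### The two zero-treatment rows (0/287 and 0/957) are shown without an interval, and infants without a final ROP outcome are not counted

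*Combined protocol and SAP*

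**What the plan says.** The data-source paragraph of the combined protocol and SAP gives the only cohort rule: "Surviving infants with birth gestational age of 21+6 weeks to 30+6 weeks are included in the analysis". The source is described as "We use a de-identified data set of examination results from 28 hospitals which employed the software from 2010 through 2022". The outcome of interest is treatment: "Data reviewed concerning those infants who progressed to threshold for therapy (Type 1) and what type of therapy delivered".

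On analysis, the opening summary says "Statistics are typical descriptive statistics from database including median, interquartile range and percentages" and then "These are analyzed with Mann-Whitney, Kruskal-Wallis and Chi Square". After the data-source paragraph it adds that "details of numbers and timing of recorded encounters (either examinations or treatments) in ROP Check® are analyzed".

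The software is described as "used for ensuring ROP exams occur in a timely manner" and "for ophthalmologist tracking ROP staging exams and treatment".

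The comparison table applies each screening rule to the 2010 to 2022 data and prints a cohort size, a treated count and a percentage treated (%Tx). The 30+4 row has 287 of 5058 infants and the ROP-if-P row 957 of 5058. Both show 0 treated and 0.0%. Of the two undefined columns for missed cases, one reads na and the other 0 in both rows.

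**The concern.** The study sets screening rules side by side, and the table invites a direct reading: two rules with zero treated, and three (Moir+, SCREEN-ROP, TWO-ROP) with 0.3%. A zero from a few hundred infants says much less than a zero from many thousands, and the table gives no limit that would show the difference.

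A second gap concerns what a zero means. Treatment can be recorded only while an infant is still being examined in the system. The documents define no final outcome (retinal maturity, regression or treatment), set no minimum length of follow-up, do not address infants discharged or transferred before an outcome, and give no count of them. They also do not say whether 2022 is the year of the last birth or of the last exam. A reader therefore cannot separate infants who were not treated from infants who were not observed to the end. This matters most in the zero rows, where one unrecorded treatment would end the result.

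**Working it through.** **Inputs.** Treated and cohort counts come from the comparison table. The inclusion rule and planned statistics come from the opening summary and the data-source paragraph. The documents give no rate of incomplete records, so every such rate below is an assumption.

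**1. Reproduce the printed percentages.** %Tx = treated / cohort. The exact (Clopper-Pearson) 95% limits for t treated of n are the 0.025 quantile of Beta(t, n−t+1) and the 0.975 quantile of Beta(t+1, n−t).

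| Row | Treated / cohort | Computed | Printed | Exact 95% limits |
|---|---|---|---|---|
| E-ROP | 32/2975 | 1.08% | 1.1% | 0.74 to 1.52% |
| First-ROP | 29/2917 | 0.99% | 1.0% | 0.67 to 1.43% |
| Moir+ | 4/1543 | 0.26% | 0.3% | 0.07 to 0.66% |
| SCREEN-ROP | 2/625 | 0.32% | 0.3% | 0.04 to 1.15% |
| TWO-ROP | 3/989 | 0.30% | 0.3% | 0.06 to 0.88% |
| Whole cohort | 387/5058 | 7.65% | 7.7% | 6.93 to 8.42% |
| 30+4 | 0/287 | 0.0% | 0.0% | 0 to 1.277% |
| ROP-if-P | 0/957 | 0.0% | 0.0% | 0 to 0.385% |

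All printed values reproduce on the full printed cohort.

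**2. Upper limits for the zero rows.** With t = 0 the upper limit is 1 − 0.025^(1/n).
- n = 957: 0.385%, about 3.9 per 1000.
- n = 287: 1.277%, about 12.8 per 1000.

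Other methods agree closely. Wilson gives 0.400% and 1.321%. The one-sided 95% bound gives 0.313% and 1.038%.

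**3. How easily would a zero arise at a rival's rate?** Take the TWO-ROP rate, p = 3/989 = 0.303%. The chance of no events is (1 − p)^n.
- n = 957: 0.0546, about 5.5%.
- n = 287: 0.418, about 42%.

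This is illustrative only. All rows come from the same 5058 infants and overlap, so they are not independent samples.

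**4. Effect of incomplete records (assumed rates).** Suppose a share of each zero row lacked a final outcome and was removed from the denominator. The upper limits become:

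| Share incomplete | ROP-if-P | 30+4 |
|---|---|---|
| 0% | n = 957: 0.385% | n = 287: 1.277% |
| 5% | n = 909: 0.405% | n = 273: 1.342% |
| 10% | n = 861: 0.428% | n = 258: 1.420% |
| 30% | n = 670: 0.549% | n = 201: 1.819% |

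If one treatment had gone unrecorded, the rows would read 1/957 = 0.104% (upper limit 0.581%) and 1/287 = 0.348% (upper limit 1.926%).

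**5. Why a rate limited to complete records also needs care.** Every treated infant has a final outcome, so only untreated infants can drop out of the denominator. If a share f of the 4671 untreated infants (5058 − 387) is incomplete, the overall rate is 387 / (387 + (1 − f) × 4671). That is 8.02%, 8.43% and 10.58% for f = 0.05, 0.10 and 0.30. The true rate would be expected between the all-infant figure and this one.

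**The case against.** Several points on the other side are fair.

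- **Treated over cohort does not prove that incomplete infants were counted as untreated.** A reader might infer this from the reproduced percentages. But 387/5058 would look the same if 5058 had already been limited to infants with finished exams, and no total database count is given. What stands is narrower: the rule as written has no such limit, and the documents do not say whether one was applied.
- **The plan does not exclude intervals.** Its list of statistics is introduced as including certain items, so it need not be exhaustive. Still, none is named and none is printed.
- **Counts and denominators are printed, so a reader can work out a limit.** True: the rule of three gives about 0.31% and 1.05%. The table should not leave this to the reader.
- **The follow-up effect may be small.** At 5 to 10% incomplete, the ROP-if-P limit moves only from 0.385% to 0.428% at most. The software's stated purpose is timely exams, which makes gaps less likely. If only births in the last four of 156 months were cut off and accrual were even (assumption), that would be 4/156, about 2.6%. However, hospitals started in different years, so even accrual is not assured.
- **An exact interval can itself mislead.** If the cut-offs of the two zero rules were chosen because they gave no treated infants here, ordinary limits on the same infants are too favourable. This stands and belongs in the fix.

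A reader might also try to trace how an unrecorded treatment would move several rows together, and so infer which rule would rank first. The printed thresholds do not allow it. With the split birth-weight cell read as 1400, ROP-if-P (above 1400, above 30 weeks) should sit inside SCREEN-ROP (above 1200, above 30 weeks), yet it has 957 infants against 625.

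**Conclusion.** The point holds in two parts of unequal certainty.

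The missing interval is established and needs no assumption about follow-up. The two-sided upper limits of 0.385% and 1.28% both exceed the point rates of Moir+, SCREEN-ROP and TWO-ROP (0.26%, 0.32%, 0.30%). The zeros alone do not show either rule to be safer than these three. For 30+4 this is clear. For ROP-if-P it is closer: the one-sided bound of 0.313% falls just under the SCREEN-ROP rate. The statement does not extend to ROP-if-P against E-ROP and First-ROP, whose lower limits (0.74% and 0.67%) lie above 0.385%.

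The follow-up part is a gap in what is stated. If the inclusion rule is applied as written, truncated records count as untreated and can only lower the treated counts. Whether any exist, and how many, is unknown. It would go too far to conclude that treatments were missed, that the zeros are false, or that the order of the rules would change.

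The change should be made. Nothing here invalidates the study.

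**What to change.** 1. Report exact 95% limits for %Tx in every row. State how the 30+4 and ROP-if-P cut-offs were chosen, and note that their limits are optimistic if they were chosen on these same infants.
2. From the recorded staging exams and encounter timing, derive a flag for a final ROP outcome (maturity, regression or treatment). Report the number of infants without one in each row.
3. Show %Tx with limits both for all included infants, which leans low if records are incomplete, and for those with a final outcome, which leans high. In the zero rows the second rate stays at zero while its upper limit widens. If 5058 was already limited to finished records, say so and give the number excluded.

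The cost is one constructed variable, which needs a written definition because the documents name no maturity or regression field, and additional columns in the table. No new data are needed. The downsides are a little more analysis, smaller denominators for the second rate, and less favourable statements for the two zero-event rules.

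### Raw misses in each rule's source are set beside raw misses in ROP Check on very different denominators, so the counts alone do not support a source-versus-ROP Check contrast

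*Combined protocol and SAP*

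**What the plan says.** The cover-page description says the AAP criteria are "evaluated in light of other recent proposals and compared to the ROP Check® dataset". The paragraph before the table gives the reason: the proposed changes were "not yet compared with a North American cohort of premature infants" with many infants of Pacific race. The population is fixed for every rule: "Surviving infants with birth gestational age of 21+6 weeks to 30+6 weeks are included in the analysis".

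The table, headed "Compared study cohorts", gives for each published rule the source's 'patients' (as n of N) and 'miss ?'. Next to these it gives ROP Check's 'missed ?', 'Avoid ?', 'Cohort', 'Treat' and '%Tx'. Misses appear only as counts. None of these columns is defined.

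On methods, the cover page says "Statistics are typical descriptive statistics from database including median, interquartile range and percentages" and "These are analyzed with Mann-Whitney, Kruskal-Wallis and Chi Square". It assigns no method to the comparison of a source with ROP Check.

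**The concern.** A reader scanning the two miss columns sees 0 or 1 become 2 to 4 in every row. The layout does not show that 0 of 61 and 0 of 6025 print as the same zero, or that the same cut-offs appear to select very different fractions of the two populations. At stake is any statement about whether published rules carry over to this cohort. Without denominators and intervals, a row holding almost no information (SCREEN-ROP) looks the same as one with a real numerical difference (1000 g / 29 wk).

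**Working it through.** **Inputs.** All come from the comparison table. The ROP Check total is 5058.

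**Reproducing a printed figure.** '%Tx' is Treat/Cohort: 32/2975 = 1.08%, 29/2917 = 0.99%, 4/1543 = 0.26%, 2/625 = 0.32%, 3/989 = 0.30%, and 387/5058 = 7.65% overall. All match the printed decimals, so 'Cohort' is the ROP Check denominator the plan itself uses.

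**Reading 'n of N'.** In the two in-house rows n equals 'Cohort' (287 and 957, each of 5058), so n is the subset above the cut-offs. I assume the same for the published rows.

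**Step 1: share above the cut-offs.** Source = n/N; ROP Check = Cohort/5058. Differences are taken before rounding.

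| Rule | Source | ROP Check | Difference (points) |
|---|---|---|---|
| E-ROP | 1257/6729 = 18.7% | 2975/5058 = 58.8% | +40.1 |
| First-ROP | 1125/2004 = 56.1% | 2917/5058 = 57.7% | +1.5 |
| 1000 g / 29 wk | 6025/8364 = 72.0% | 1543/5058 = 30.5% | −41.5 |
| SCREEN-ROP | 61/823 = 7.4% | 625/5058 = 12.4% | +4.9 |
| TWO-ROP | 1095/3239 = 33.8% | 989/5058 = 19.6% | −14.3 |

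**Step 2: misses on own denominators.** Clopper-Pearson 95% intervals; two-sided Fisher exact test.

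| Rule | Source | ROP Check | p |
|---|---|---|---|
| E-ROP | 1/1257 = 0.080% (0.002 to 0.442) | 4/2975 = 0.134% (0.037 to 0.344) | 1.00 |
| First-ROP | 0/1125 (0 to 0.327) | 4/2917 = 0.137% (0.037 to 0.351) | 0.58 |
| 1000 g / 29 wk | 0/6025 (0 to 0.061) | 4/1543 = 0.259% (0.071 to 0.662) | 0.0017 |
| SCREEN-ROP | 0/61 (0 to 5.9) | 2/625 = 0.320% (0.039 to 1.151) | 1.00 |
| TWO-ROP | 0/1095 (0 to 0.336) | 3/989 = 0.303% (0.063 to 0.884) | 0.11 |

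With whole cohorts as denominators (N and 5058) the p-values are 0.17, 0.58, 0.020, 1.00 and 0.29, in the same order.

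**Step 3: what a zero in the source is worth.** The chance of no misses at the ROP Check rate, taken as known, is (1 − rate)^n:
- SCREEN-ROP: (1 − 2/625)^61 = 0.82
- First-ROP: (1 − 4/2917)^1125 = 0.21
- TWO-ROP: (1 − 3/989)^1095 = 0.036. Fisher's 0.11 is larger because it allows for the uncertainty in 3/989.
- 1000 g / 29 wk: expected misses 6025 × 4/1543 = 15.6, and the chance of none is about 2 × 10⁻⁷.

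**Step 4: are the rules applied as printed?** BW>1500 with GA>30 (TWO-ROP) should select a subset of BW>1200 with GA>30 (SCREEN-ROP). The table gives 989 and 625 from the same 5058 infants. The printed cut-offs therefore cannot be the full criteria applied in both rows. Across sources, the stricter 1000 g / 29 wk cut-offs select 72.0% while the looser E-ROP cut-offs (750 g / 27 wk) select 18.7%. Either the sources differ in eligibility, or criteria are unprinted, or 'n of N' changes meaning between rows.

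**The case against.** The strongest reply is that the documents never say the rules do worse in ROP Check. The study is descriptive, and how many infants a rule misses in ROP Check is informative without any source comparison. That stands. A reader might infer from the adjacent columns that every published rule fails here, but no sentence in the plan says so.

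A second tempting reading is that the gap in exempt share produces the difference in misses. The table does not support this. First-ROP's shares nearly match, so sparse counts are the issue there. For the 1000 g / 29 wk rule and TWO-ROP the source has the larger denominator and still no misses, so denominators widen the gap. Case mix is not examined at all.

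Third, the word 'exempt' is doubtful for some rows. '1st exam?' shows 37, 34 and 38-9 wk for E-ROP, First-ROP and TWO-ROP, which looks like deferral. E-ROP and First-ROP list 32 and 29 treated against 4 missed. 'Avoid ?' is 2.0% for E-ROP against a share of 58.8%, whereas the in-house rows show 2.5% against 5.7% and 7.9% against 18.9%. This stands too: the shares in Step 1 are conditional, and the groups are better called infants above the cut-offs.

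Finally, one fixed ROP Check population lets the rules be compared with each other. A different subset per rule as the main analysis would lose that. I agree.

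**Conclusion.** The point holds as one about reporting and interpretation. Raw counts on denominators from 61 to 6025 do not support a source-versus-ROP Check contrast. For four rules the data show no detectable difference, which with 0 to 4 events per side is not evidence of equal performance. For the 1000 g / 29 wk rule there is a nominal difference (p = 0.0017; 5 × 0.0017 = 0.0085 after a Bonferroni adjustment for five rows). It cannot be attributed to the rule, because population, era, ascertainment or coding could each explain it. The share gaps of +40.1 and −41.5 points rest on reading 'n of N' as the subset above the cut-offs. If that fails in a published row, that row's source rate is not available as printed. The conflict between 989 and 625 needs no such reading of the source columns. It requires only that 'Cohort' counts the infants each rule selects, as in the in-house rows.

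**What to change.** 1. Define 'patients', 'miss ?', 'missed ?', 'Avoid ?' and 'Cohort'. Replace raw misses with n/N and exact 95% intervals on both sides, using as denominator the infants to whom the rule applies. Label deferral rules as deferral, not exemption.
2. Print the share above the cut-offs for the source and for ROP Check.
3. Verify and state the full criteria applied for each rule, starting with TWO-ROP and SCREEN-ROP, whose printed cut-offs and counts conflict.
4. Keep the 21+6 to 30+6 week population as the main analysis. Add restriction to each source's eligibility only as a sensitivity analysis, where those criteria are available. Limit conclusions to performance in ROP Check unless the populations are shown to be comparable.

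Cost: changes to SAP and table wording and a short re-run on existing data, with no new ROP Check data. The source criteria must be looked up for the sensitivity analysis, and its subsets will be smaller. The claim about transfer of the rules becomes weaker.
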